8.2.1.3. Change in HbA1c from baseline to week 24 by eGFR status

They will be tested following the hierarchical order specified in section 8.2. They will be analyzed using the same MMRM ANCOVA model stated in section 8.1.1.

8.2.2. Exploratory secondary efficacy endpoints and analyses

All endpoints in this section are exploratory. No sensitivity analyses and adjustment for multiple comparisons will be conducted. Nominal p-values will be used to examine any trends in these endpoints.

8.2.2.1. Changes from baseline in HbA1c, body weight, SBP, diastolic BP, FPG, and albuminuria over time

The schedule of HbA1c, body weight, SBP, diastolic BP, and FPG over time can be found in Table 1. The absolute value and change from baseline during the double-blind treatment period will be summarized by descriptive statistics at each visit. Change from baseline in HbA1c will be analyzed as part of primary efficacy analysis. The change from baseline in body weight, SBP, and FPG will be analyzed using the MMRM ANCOVA model from primary analysis as a template (Section 8.1.1). The fixed effect will include region, baseline HbA1c level as continuous variable, screening anti-diabetic treatment regimen (insulin treated or other), baseline eGFR (<45 or ≥ 45 mL/min/1.73m²), treatment, visit, and treatment-by-visit. The appropriate baseline values will be used as covariate. LS means for each treatment and the difference between treatments will be estimated at each visit. The

corresponding p-values will also be presented.

All values for follow-up visits will be listed.

8.2.2.2. Change in albuminuria from baseline to week 24

Descriptive statistics for geometric mean, geometric coefficient of variation (gCV), median, Q1, Q3, minimum, and maximum of UACR values will be presented at baseline, and week 24 for all subjects and for baseline macroalbuminuria subjects (>300 mg/g). UACR data is left-skewed and will be natural log transformed first. Change in log transformed UACR from baseline to week 24 will be analyzed by ANCOVA model. The fixed effect will include region, baseline HbA1c level as continuous variable, screening anti-diabetic treatment regimen (insulin treated or other), baseline eGFR (<45 or ≥ 45 mL/min/1.73m²), and treatment. The log transformed baseline values will be used as covariate. Analysis will be repeated for baseline macroalbuminuria subjects. LS means for each treatment and the difference between treatments will be estimated at week 24. The adjusted geometric mean ratio of relative change from baseline in UACR (the ratio of the week 24 geometric mean and baseline geometric mean) and the corresponding two sided 95 % CI by treatment group will be calculated as the antilog of the LS mean and 95 % CI of log transformed values, converted to percentage. The adjusted geometric mean ratios of relative change from baseline in UACR for bexagliflozin vs. placebo (ratio of the two ratios obtained from previous steps) and their 95% CI will be calculated as the antilog of the LS mean differences and their 95% CI. Sample SAS code will be provided in Appendix 21.2.

8.2.2.3. Proportions of subjects with HbA1c of < 7% over time and proportion of $\geq 5\%$ reduction of body weight in subjects with baseline BMI ≥ 25 kg/m² at week 24

Summary on the proportion of subjects achieving HbA1c < 7% at each visit and the proportion of $\geq 5\%$ reduction of body weight during each visit interval will be presented over time. They will be analyzed using generalized estimating equation (GEE) logistic regression. The fixed effect will include region, baseline HbA1c level, screening anti-diabetic treatment regimen (insulin treated or other), baseline eGFR (<45 or ≥ 45 mL/min/1.73m²), treatment, visit, and treatment-by-visit. An unstructured correlation structure will be used (or autoregressive [1] if the model with the unstructured structure does not converge). The LS mean proportion for each treatment will be estimated at each post-baseline visit. The odds ratios of bexagliflozin group over the placebo group at each visit and across all post-baseline time points will be estimated from LS means based on the model with the corresponding p-values and their two-sided 95 % CIs presented. Similar method will be used for analyzing proportion of subjects with body weight reduction $\geq 5\%$ in subjects with baseline BMI ≥ 25 mg/m². Baseline body weight will be added to the model as a

covariate. Sample SAS code will be provided in Appendix.

9. SAFETY

The analysis population used for safety analyses will be the Safety Analysis Set. Safety data include AEs; physical examination results; vital signs, including blood pressures; ECG results; and clinical laboratory results, including serum chemistry, hematology, serum lipids, and urinalysis.

Observed data will be summarized by treatment group as counts and percentages for discrete variables and means, SDs, medians, minimum, and maximum for continuous variables. All subjects who are randomized and receive at least one dose of double-blind study medication will be included in the safety analysis. All safety data will be presented in by-subject listings and included in the clinical trial report.

9.1. EXTENT OF EXPOSURE

Study drug exposure will include:

- Treatment duration by treatment group
- Total dose taken by treatment group

Treatment duration of tablets (in weeks) is calculated as (the date of the last dose of study drug - the date of the first dose of study drug + 1) / 7 and rounded to 1 decimal place.

The specific definitions of the first dose and last dose dates of study drug are given below:

- First dose date: The date of the first dose of study treatment during the double-blind treatment period obtained from the study drug exposure CRF.
- Last dose date: The date of the last dose of study medication in the 24 week treatment period for subjects who have completed the study or discontinued early.

Total dose taken will be calculated as number of tablets dispensed - number of tablets returned. If any of the bottles dispensed is not returned, it will not be possible to compute the total dose received. In this case, the number of tablets taken will be considered as missing. Summary statistics for total dose taken will be provided by treatment group for the double-blind treatment period.

Summary statistics for treatment duration (in weeks) and a frequency summary of treatment duration categories (e.g., ≥ 1 Day, ≥ 6 weeks), will be provided.

9.2. TREATMENT COMPLIANCE

Subjects will be provided with dosing instructions each time study medication is dispensed. Subjects will also be instructed to bring their medication with them to every visit. During the run-in period, subjects will be considered compliant in investigational product administration by missing no more than one dose of run-in medication. Subjects who are not compliant during the run-in period will be excluded from randomization.

At each visit the study staff will review the self-monitored blood glucose (SMBG) control diary, glucometer data and medication use with the subject and record the drug consumption in the CRF. Reasons for non-adherence will also be recorded in the protocol deviation log if applicable.

Compliance in the run-in and double-blind phase is calculated for as follows:

- Percent compliance = (number of tablets taken / number of tablets should have taken) x 100.
- Number of tablets taken = number of tablets - number of tablets returned.
- Number of tablets should have taken = (number of tablets supposed to take in a day) x (number of exposure days).
- Number of exposure days = last dose date - first dose date + 1.

If any of the bottles dispensed is not returned, it will not be possible to compute the compliance. In this case, the number of tablets taken and compliance will be considered as missing. Summary statistics for tablet or capsule compliance (%) will be provided by treatment group for the double-blind treatment period. A frequency summary of compliance will also be presented with the following categories: < 75%, 75% - < 100%, 100% - ≤ 120%, and > 120%.

9.3. ADVERSE EVENTS

Adverse events will be collected and recorded from the time a subject signs the informed consent form (ICF) to the last scheduled contact. And new SAE reported by the subject to the investigator that occur after the last scheduled contact, and are determined by the investigator to be reasonably associated with the use of the investigational product, should be reported to the sponsor or designated personnel. This may include SAEs that are captured on follow-up telephone contact or at any other time point after the defined study period (i.e., up to last scheduled contact). The investigator should follow SAEs identified after the last scheduled contact until the events are resolved, or the subject is lost to follow-up. The investigator should continue to report any significant follow-up information to the sponsor until the event

has been resolved. This study requires that subjects be actively monitored for SAEs for at least 4 weeks after the last treatment.

For all AEs, preferred AE terms and system organ class (SOC) will be coded using terminology from the Medical Dictionary for Regulatory Activities (MedDRA), version 19.0 or higher.

A treatment-emergent adverse event (TEAE) is defined as an AE that begins after the first administration of double-blind study medication or existing AEs that worsen after the first dose of double-blind study medication. All reported AEs will be listed, but only TEAEs will be summarized in tables.

Drug-related AEs will be considered those to be possibly, probably and definitely related to IP administration based on the investigators assessment.

Unless otherwise specified, AEs will be summarized by SOC and PT, with SOC and PTs within SOC presented in descending order of subject incidence.

9.3.1. Derived Data

AE onset day is calculated as (date of AE start - date of double-blind first dose + 1) if it is after the first dose of study drug. AE onset day is calculated as (date of AE start - date of double-blind first dose) if it is before the first dose of study drug.

9.3.2. Data Summarization

AE summary tables are listed below:

- An overall summary of the number and percentage of subjects reporting any TEAEs, serious TEAEs, treatment-related TEAEs, serious treatment-related TEAE, any TEAEs leading to treatment discontinuation, any TEAEs leading to subject discontinuation and TEAEs leading to death.
- TEAEs overall and by SOC and PT
- TEAEs by severity, overall and by SOC and PT
- Serious TEAEs, overall and by system organ class and preferred term
- TEAEs by relationship to study treatment, overall and by system organ class and preferred term
- TEAEs leading to treatment discontinuation, overall and by SOC and PT

- TEAEs leading to study discontinuation, overall and by SOC and PT
- Most common TEAEs. Most common TEAEs are defined as TEAEs that occur in > 5% of the subjects in either of the treatment groups.

For summary tables, subjects having more than 1 event with the same PT will be counted once for that term. Subjects having more than 1 event with the same SOC will be counted once for each event and once for that SOC. For tabulations by severity, only a subject's most severe event within the category (e.g. overall, SOC, PT) will be counted; similarly, for tabulations by relationship, only a subject's most related event within a category will be counted. The denominator for percentages will be the number of subjects in the Safety Analysis Set for the given treatment group (i.e., the N's for the columns).

Listings will be provided for all AEs and the following subsets:

- Serious AEs
- AEs leading to treatment discontinuation
- AEs leading to death.

9.3.3. AE of Special Interest

AE of special interest include UTI, GMI, diuretic effects, hepatotoxicity, MACE, hypoglycemia, fracture, malignancy, hypersensitivity reactions, hypotensive episodes, acid base disorders, DKA, renal failure events, and amputations. The AEs of special interest, except for MACE and amputations, will be prospectively identified based on the MedDRA PTs in the AEs log by a medical expert prior to the data base lock and unblinding of the individual subject treatment assignment. The list of AEs of special interest will be confirmed in a peer review process. Adjudicated MACE will be summarized in the same AE of special interest table. Hypoglycemia events by severity, and amputations will be summarized separately. Additional information will be collected for DKA. These data will be listed if available.

9.3.3.1. AE of special interest identified by PTs

Cardiovascular events considered as MACE by investigator will be submitted to an independent Cardiovascular Endpoint Committee (CEC) for adjudication. The events of interest include cardiovascular mortality, MI, stroke, hospitalization for acute coronary syndromes, urgent revascularization procedures, and other possible serious cardiovascular events. Other AE of special interest will be identified from the PTs. The number and percentage of subjects experiencing these TEAEs of special interest will be summarized for each treatment group by type of event. The incidence rate of AE of special interest per 100 patient years will also be summarized. It will be

calculated as total number of AEs / total patient years in specific treatment arm (or total) * 100. Each category of events will be displayed in a separate listing.

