9.8.1 Adverse Events

Adverse events will be mapped to preferred term and body system using the Medical Dictionary for Regulatory Activities (MedDRA). AE records that begin at or after the first administration of investigational products are considered treatment emergent AEs (TEAEs). The number and percentage of subjects reporting TEAEs will be summarized for each treatment group by MedDRA system organ class and preferred term. Further summaries by severity, and by relationship to study treatment will also be provided. Drug-related AEs will be considered those to be at least possibly related to investigational product based on the investigator's assessment. The number and percentage of subjects reporting serious AEs, and the number and percentage of subjects reporting AEs leading to treatment discontinuation will also be summarized for each treatment group by MedDRA system organ class and preferred term.

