3.5. BRIEF DESCRIPTION

THR-1442-C-448 is a phase 3, multi-center, randomized, double-blind, placebo-controlled, parallel-group study to evaluate the efficacy and safety of oral administration of bexagliflozin at 20 mg versus placebo in subjects with T2DM, moderate renal impairment, and inadequate glycemic control.

Main eligibility criteria include: 1) male or female subjects with T2DM, 2) screening HbA1c of 7.0-10.5% (inclusive), and 3) estimated glomerular filtration rate (eGFR) based on serum creatinine at 2 different assessments ≥ 30 to < 60 mL/min/1.73 m² based on the serum creatinine at the screening visit and one additional time point between 1 and 12 months prior to screening (may be obtained from available medical records. The eGFR will be calculated by the modification of diet in renal disease study equation (MDRD). At the time of screening, the doses and frequency of all anti-diabetic medications must have been stable for 8 weeks.

All eligible subjects will enter a one week single blind, placebo run-in period to allow for diabetes education and optimization of compliance with diet and exercise recommendations. Subjects who are compliant in taking run-in medication (missing no more than one dose), have screening eGFR ≥ 30 to < 60 mL/min/1.73 m², and have stable GFR (no more than 20% change in eGFR between a historical value and the value determined at the screening visit V1) will be eligible for randomization and receive study drug.

Approximately 300 subjects will be randomly assigned in equal ratio to receive once daily bexagliflozin tablets, 20 mg or placebo, in equal ratio once daily for 24 weeks in an outpatient setting. Randomization will be stratified by screening HbA1c level (7.0 to 8.5% or 8.6 to 10.5%), screening anti-diabetic treatment regimen (insulin treated or other) and screening eGFR (30 - 44 mL/min/1.73 m² or 45 - 59 mL/min/1.73 m²). At least 135 subjects in each of the eGFR groups must be enrolled.

Study subjects will have scheduled visits at weeks 2, 6, 12, 18, and 24 for safety and efficacy evaluation. At weeks 2 and 18, the visit will be conducted via phone interviews unless clinically necessary. A final follow up visit will be conducted at week 26 or two weeks after last dose of study drug if the subject terminates prior to Week 24.

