6.2.4. Duration

Duration of double-blind treatment will be determined as Double-Blind Duration = Double-Blind Last Dose Date minus Double-Blind First Dose Date plus 1. Duration of Run-In period will be determined as Last Dose Date in the run-in period minus First Dose Date in the run-in period plus 1.

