6.2.6. Patient Years

Patient years are calculated as sum of the duration of double-blind treatment / 365.24 of all subjects in the specified analysis set and treatment arm. This is used as the denominator of the computation of incidence rate.

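### The AESI rate per 100 patient-years counts events to last contact but person-time only to last dose, so it is about 8% to 9% above the rate over the same follow-up: a small, descriptive error that is cheap to fix

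*SAP*

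**What the plan says.** **Denominator.** SAP 6.2.6: "Patient years are calculated as sum of the duration of double-blind treatment / 365.24 of all subjects" in the analysis set and arm. The same section names this as the denominator for incidence rates. SAP 6.2.4 defines the duration: "Double-Blind Duration = Double-Blind Last Dose Date minus Double-Blind First Dose Date plus 1". SAP 9.1 describes the last dose date as "The date of the last dose of study medication in the 24 week treatment period". Time after the last dose is therefore left out.

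**Numerator.** SAP 9.3.3.1 gives the rate as "total number of AEs / total patient years in specific treatment arm", multiplied by 100. It applies to AESIs identified by preferred term, and SAP 9.3.3 puts adjudicated MACE in the same table. SAP 9.3 defines a treatment-emergent event as "an AE that begins after the first administration of double-blind study medication or existing AEs that worsen after the first dose" of double-blind drug. Protocol 9.8.1 also gives only a start. Neither definition has an end date. SAP 9.3 collects events "from the time a subject signs the informed consent form (ICF) to the last scheduled contact". SAP 3.5 places the final visit at "week 26 or two weeks after last dose of study drug if the subject terminates prior to Week 24", and Protocol 3.2.3 agrees.

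**Longer follow-up off drug.** Protocol 6.18 encourages subjects who stop the product to stay in the study. Protocol 6.16.12 follows everyone for MACE for the study duration, even after permanent withdrawal of drug. SAP 9.3 and Protocol 6.16.7 require active SAE monitoring for at least four weeks after the last treatment.

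Protocol 9.8.2 asks for the rate per 100 patient-years but does not define it, so the SAP formula is the only definition.

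**The concern.** A rate per 100 patient-years should relate events to the time in which they could have been observed. Here the two parts of the fraction cover different periods. The numerator includes events that start in the off-drug follow-up, and the denominator excludes that follow-up.

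Off-drug events can be expected. The week 26 visit includes adverse event and DKA assessment, diary review, blood chemistry and urinalysis (Protocol 7.9 and Appendices 1 and 2), so events can be first recorded there.

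At stake is the absolute level of the exposure-adjusted rates for preferred-term AESIs and adjudicated MACE. A reader would take them as events per time at risk, and by the stated formula they are not.

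**Working it through.** The documents give no AESI rate or patient-year total, so there is no planned figure to reproduce.

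**Inputs from the documents**
- Planned treatment: 24 weeks = 168 days (Protocol 3.4).
- Off-drug follow-up to the exit visit: 2 weeks = 14 days (SAP 3.5, Protocol 3.2.3).
- Early termination: 12% (SAP 8.1.2).
- 150 subjects per arm (SAP 3.7); 365.24 days per year (SAP 6.2.6).

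**Assumptions**
- Early terminators stop at week 12 (84 days) on average.
- The off-drug event rate is r times the on-drug rate. The documents give no r, so 0 to 1 is shown.

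**Formulas.** Let T_on be mean days on drug, T_off mean days of off-drug follow-up, and E all events counted.
- Reported rate: E / T_on.
- Rate over the whole follow-up window: E / (T_on + T_off).
- Reported ÷ whole-window rate = (T_on + T_off) / T_on. This does not depend on r, provided there are any events.
- Reported ÷ on-drug rate = 1 + r × T_off / T_on.

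**Against the whole-window rate**
- All complete: (168 + 14)/168 = 182/168 = 1.083, so 8.3% too high.
- 12% stop at week 12, with a two-week exit visit: T_on = 0.88 × 168 + 0.12 × 84 = 157.92; T_on + T_off = 0.88 × 182 + 0.12 × 98 = 171.92; 171.92/157.92 = 1.089, so 8.9% too high.
- Other mean stopping times for the 12%: week 18 gives 14/162.96 = 8.6%; week 0 gives 14/147.84 = 9.5%.

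**Against the on-drug rate**

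| r (assumed) | All complete | 12% stop at week 12 |
|---|---|---|
| 0 | 0% | 0% |
| 0.5 | 7/168 = 4.2% | 7/157.92 = 4.4% |
| 1 | 14/168 = 8.3% | 14/157.92 = 8.9% |

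**Scale per arm, all complete.** Counted: 150 × 168/365.24 = 69.0 patient-years. Left out: 150 × 14/365.24 = 5.75. At an illustrative constant rate of 20 per 100 patient-years there are 13.8 on-drug and 1.15 off-drug events, and the reported rate is 14.95/69.0 = 21.7 per 100.

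**Where 14 days is not the right length.** With the ±3-day visit windows (SAP 3.10), a completer's off-drug follow-up can run from 8 days (day 171 to 179) to 20 days (day 165 to 185). If serious events found through the four-week monitoring entered the numerator, the figure for those events at r = 1 would be 28/168 = 16.7% (all complete). The SAP does not say whether they do.

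**Between-arm ratio.** With equal stopping, the factor (T_on + T_off)/T_on is the same in both arms and cancels. With unequal stopping at week 12 and a two-week exit visit:
- 12% v 6%: (171.92/157.92)/(176.96/162.96) = 1.0025.
- 20% v 10%: (165.2/151.2)/(173.6/159.6) = 1.0045.

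**The case against.** **It is only descriptive.** This stands. SAP 9.3.3.1 also gives the number and percentage of subjects with each event, and no test or decision rule uses the rates. In the illustration, the Poisson standard deviation of 13.8 events is 3.7, or 27%, so an 8.3% shift is under a third of one standard error. SAP 6.2.6 also states the denominator openly.

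**If nothing happens off drug, the reported rate is already the exact on-drug rate.** This also stands. Widening the denominator would then lower it by 7.7% (168/182 = 0.923). The size of the error depends on which rate is the target, and the SAP does not name one.

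**The cut-off may be in the attachments.** The table shells and SAS code (SAP 20 and 21.2) were not available. A cut-off there would cure the calculation, but it would narrow the numerator that SAP 9.3 and 9.3.3.1 describe, so the text would still need correcting.

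**Stronger readings that the documents do not support**
- A reader might infer that the mismatch hides drug-related signals by pulling between-arm ratios toward 1. Such a pull can arise when off-drug events are counted at all and the event rate falls after stopping. It is not caused by the mismatched denominator: for completers, dividing both arms by 168 or both by 182 days gives the same ratio.
- A reader might take about 9% as a ceiling. It is not one, because some subjects are followed longer off drug.
- A reader might apply the 12% to subjects who stop drug but stay to week 26, and so obtain larger figures. The 12% is the early termination rate, which describes a different group, and the documents give no figure for those who stay.

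**Conclusion.** The SAP text pairs a numerator that runs to last contact with a denominator that ends at last dose, and no visible passage in either document reconciles them. As written, the AESI rate is not events per time at risk.

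Relative to the whole-follow-up rate, the excess of 8.3% to about 8.9% rests on a nominal two-week exit visit and, for the upper figure, on an assumed mean stop at week 12. Relative to the on-drug rate, the range from 0% to about 8% to 9% rests on an assumed off-drug event rate between zero and the on-drug rate. The excess is larger for subjects who stop drug but stay in the study, and for serious events if those sought to four weeks are counted. Neither excess can be sized for this trial from the documents.

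The consequence is minor: absolute rates for preferred-term AESIs and adjudicated MACE are somewhat too high. The point is worth making because the definition is wrong as written and easy to put right.

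**What to change.** In SAP 6.2.6 and 9.3.3.1, use one window for both events and person-time. One option is first dose to the earlier of last dose plus 14 days and the end-of-study date (SAP 6.2.5). The cap at 14 days handles the visit windows and subjects who stay on after stopping drug; the end-of-study date handles those who leave sooner.

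- For MACE, which the protocol follows off drug, also give a rate with events and person-time both running from first dose to the end-of-study date.
- List serious events that fall after the window separately, so that those found through the four-week monitoring remain visible without entering the rate.
- Name the window in the footnote of Table 14.3.1.9, and check that the table shells and SAS code follow it.

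The cost is SAP wording and minor programming. The last-dose and end-of-study dates are already collected. Reported rates become slightly lower, and MACE has two rates instead of one.
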